2	12 Aug 2019	Obsolete	Change the type of reinforcement tape used, correct SAE definition 2, correct question #4 and completion timing for Day 0 of the Self-Assessment Questionnaire, correct Screen Failure language, and clarify a few procedures in section 7 to match the Schedule of Events in Table 2.	See Summary of Changes in Appendix VIII.
3	20 Aug 2019	Obsolete		See Summary of Changes in Appendix IX.
4	28 Aug 2019	Issued	Continue clinical grading of wound healing parameters until Day 16 for all wound sites.	See Summary of Changes in Appendix X.

[Remainder of Page Intentionally Left Blank]

Different Adhesive Bandages Protocol Number: CCSTOH001689

Version & Date: Amendment 3: Final Version 4.0, 28 Aug 2019

SYNOPSIS

PROTOCOL TITLE	A 28-Day, Single-Center, Randomized, Comparator-Controlled, Proof- of-Principle Study to Assess Wound Healing Efficacies of Different Adhesive Bandages			
PROTOCOL NUMBER	CCSTOH001689			
SPONSOR	Johnson & Johnson Con [name]		USA	
STUDY SITE	Thomas J. Stephens & Associates, Inc., Dallas Research Center [name]			
PRINCIPAL INVESTIGATOR (PI)	[name]. Address: Refer to Study	Site address		
SUB-INVESTIGATOR (SUB-I):				
STUDY PHYSICIAN/SUB-INVESTIGATOR (SUB-I):				
OBJECTIVE	The objective of this study is to assess the wound healing efficacy (time to complete healing) of different adhesive bandages.			
STUDY DESIGN	Single center, randomize clinical trial.	ed, comparator-co	ontrolled, proof-of-principle	
STUDY POPULATION	 Healthy subjects who meet the eligibility criteria, including: Males or females, 25 – 55 years old. Fitzpatrick Skin Types II-III Uniform skin color on both volar forearms 			
SAMPLE SIZE	A sufficient number of subjects will be screened to enroll as many as 40 qualified subjects to ensure completion of 30 subjects.			
	Treatment Code/Identification	UPC/PR#	Product type	
INVESTIGATIONAL STUDY MATERIALS	"Bandage" A – H (as randomly assigned by Sponsor)		N/A – uncovered wound; Negative Control Investigational Product (IP) –	
	assigned by Sportsory		IP – Benchmark Control 1	

Version & Date: Amendment 3: Final Version 4.0, 28 Aug 2019

		IP – Benchmark Control 2 IP IP IP IP Auxiliary Product	
DOSE AND MODE OF APPLICATION	The auxiliary product will be provided to to on their forearms and for all body cleans body cleanser for the duration of the study. The IPs will be applied to 7 of the 8 wou Baseline (Day 0) by trained staff act randomization scheme. The last wound so an untreated control. IPs* will be removed at the beginning of (Visit 3) through Day 16 (Visit 18) and report study visit from Day 1 (Visit 3) through Day 16 (Visit 3)	ing in place of their regular dy. Ind sites for each subject at cording to a preassigned ite will be left uncovered as each study visit from Day 1 placed** at the end of each by 15 (Visit 17).	
STUDY DURATION	The study will be conducted over approximately 5 weeks with visits at Screening (Day -7 to Day -3), daily from Baseline (Day 0) to Day 16, on Day 21, and at the end of the study on Day 28.		
METHODOLOGY	 Clinical Grading of Wound Healing Parameters (erythema, edema, epithelial confluence, crusting/scabbing, smoothness, and general wound appearance) Scarring Assessment TEWL Measurements Self-Assessment Questionnaire 		
MEASUREMENT AND/OR EVALUATION SCHEDULE AND ASSOCIATED SUCCESS	The following evaluations will be conducted the indicated time points: • Clinical Grading of Wound Healing P		

Different Adhesive Bandages Protocol Number: CCSTOH001689

Version & Date: Amendment 3: Final Version 4.0, 28 Aug 2019

	 and general wound appearance) – Day 0 through Day 16* Scarring Assessment - Day 0 and Day 28 TEWL Measurements - Day 0 through Day 14* Self-Assessment Questionnaire - Day 0 through Day 4
	Success Criterion: •
	All statistical analyses will be performed using the Statistical Analysis System (SAS) v9.4 software. The statistical analysis will be performed by the Biostatistics Group at the Sponsor. All collected assessment data will be listed individually for all subjects. The following descriptive statistics will be presented: mean, standard
STATISTICAL METHODS	deviation (SD), median, minimum, and maximum. Percentage change from baseline will also be presented. The primary endpoint, time to complete healing, is defined as the time (in days) elapsed from the time of wound creation to 12PM of the day on which the wound is evaluated as "completely healed."
	Time to complete healing will be analyzed using a survival analysis method. The survival function (cumulative percentage of wounds healed at each time point) will be estimated by the Kaplan-Meier (KM) method for each treatment separately. The median time to complete healing will be derived from the estimated survival function and be compared using the bootstrap re-sampling method.

Different Adhesive Bandages Protocol Number: CCSTOH001689

Version & Date: Amendment 3: Final Version 4.0, 28 Aug 2019

LIST OF ABBREVIATIONS

Abbreviation	Definition	
3D	Three-Dimensional	
A.A.S.	Associate of Applied Science	
AE	Adverse Event	
BLT	Benzocaine/Lidocaine/Tetracaine	
cm	Centimeter	
cm ²	Centimeter Squared	
C.M.L.S.O.	Certified Medical Laser Safety Officer	
CRF	Case Report Form	
DPR	Designated Physician Representative	
EDC	Electronic Data Capture	
EIU	Exposure In Utero	
Er:YAG	Erbium: Yttrium Aluminum Garnet	
f	Focal Length	
FDA	US Food and Drug Administration	
g	Gram(s)	
h	Hour	
HIPAA	Health Insurance Portability and Accountability Act	
ICD	Informed Consent Document	
ICH GCP	International Council for Harmonisation Good Clinical Practice	
ID	Identification	
IEC	Independent Ethics Committee	
IP	Investigational Product	
IRB	Institutional Review Board	
ITT	Intent-to-Treat	
J	Joules	
kHz	Kilohertz	
KM method	Kaplan-Meier Method	
LLC	Limited Liability Company	
m ²	Meter Squared	
M.D.	Doctor of Medicine	
mg	Milligram	
mm	Millimeter	
nm	Nanometer	
Ph.D.	Doctor of Philosophy	
PI	Principal Investigator	
PQC	Product Quality Complaint	
PTAE	Pre-Treatment Adverse Event	
SAE	Serious Adverse Event	
SD	Standard Deviation	
SEM	Standard Error of the Mean	
SM	Study Manager	
SMF	Site Master File	

Different Adhesive Bandages Protocol Number: CCSTOH001689

Version & Date: Amendment 3: Final Version 4.0, 28 Aug 2019

Abbreviation	Definition
SPF	Sun Protection Factor
TMF	Trial Master File
μm	Micrometer
W	Watt

Version & Date: Amendment 3: Final Version 4.0, 28 Aug 2019

TABLE OF CONTENTS

1.	INTRODUCTION					
2.	OBJEC	TIVE	11			
3.	STUDY	DESIGN	12			
4.	SUBJE	CT SELECTION AND ENROLLMENT	12			
	4.1.	INFORMED CONSENT	13			
	4.2.	STUDY POPULATION	13			
	4.2.1.	Inclusion Criteria	13			
	4.2.2.	Exclusion Criteria	14			
	4.2.3.	Subject Responsibilities	15			
	4.3.	CONCURRENT PRODUCTS	16			
	4.4.	CONCURRENT/CONCOMITANT MEDICATION	16			
	4.5.	SCREEN FAILURE	16			
5.	SAMPL	LE SIZE	16			
6.	INVEST	TIGATIONAL STUDY MATERIALS	16			
	6.1.	IDENTITY OF INVESTIGATIONAL STUDY MATERIALS	17			

1. INTRODUCTION

The primary goal in wound care is to protect the wound from further damage and to facilitate healing by providing the optimal environment that limits infection, inflammation and scarring. Appropriate wound dressings play an important role in providing this necessary protection and may promote restoration of skin barrier function compared to untreated wounds.¹

Wound healing is a complex process wherein the skin surface and the underlying tissue must go through an intricate process of tissue repair. The dermis of an uncovered wound is relatively more fibroplastic, fibrotic, and scarred compared to occluded wounds, and is likely to be more inflamed and necrotic in early stages of repair. Exudate, the moisture secretion from the wound site, facilitates the healing process, by providing a variety of bioactive mediators such as enzymes, growth factors and hormones. Wound exudate may also aid in limiting inflammation by providing various immune cells with an ideal medium to destroy invading pathogens such as bacteria, foreign bodies and necrotic tissues. However, exudate in an uncovered wound can lead to scab formation, with trapped inflammatory cells, wound debris, and a layer of desiccated dermal tissue. Covering a wound with an occlusive dressing reduces scab formation and may radically alter the pattern of epidermal wound healing.

Another factor that plays an important role in wound healing is the moisture in the wound environment. As early as 1962, Winter et al., provided the first evidence that keeping wounds moist helps them heal faster compared to dry wounds.²

As occlusion affects both the epidermis by enhancing epithelial cell migration and the dermis by enhancing dermal collagen synthesis, maintaining a moist environment may promote the restoration of epidermal barrier function and overall wound healing while making dressing changes relatively easier. Moreover, it has been suggested that the scar left by an occlusively dressed wound is more cosmetically acceptable than that left by an uncovered wound.³

2. OBJECTIVE

The objective of this study is to assess the wound healing efficacy (time to complete healing) of different adhesive bandages.

Different Adhesive Bandages Protocol Number: CCSTOH001689

Version & Date: Amendment 3: Final Version 4.0, 28 Aug 2019

3. STUDY DESIGN

This is a single center, randomized, comparator-controlled, proof-of-principle clinical trial. The target population is 25- to 55-year-old males and females of Fitzpatrick skin types II-III who have uniform skin color on both volar forearms. A sufficient number of subjects will be screened and enrolled to ensure completion of at least 30 subjects.

At Screening (Visit 1; 3 to 7 days prior to Baseline), subjects will be provided with an auxiliary cleanser to use on their forearms and for all body cleansing in place of their regular body cleanser for the duration of the study.

At Baseline (Visit 2), a Sciton Er:YAG 2940 laser will be used to induce eight partial-thickness (i.e. minor) wounds on the subjects' forearms (four per arm).⁴ The wounds created by this method heal by the migration of epidermal cells from the dermal appendages located in the wound's base (dermal islands) and/or wound borders, and mimic minor wounds similar to real life scraped skin, typically healing in at less than 14 days if left untreated, based on the Site's previous experience.

Each wound site will be	and assessed at pre-specified intervals by clinical
grading of wound healing parameters (until Day 16),	
In addition, subjects will assess the wound site	es via questionnaire from Day 0 to Day 4,
Between Baseline and Day 16, each wound site will	, ,
treatments (see section 6) until day of complete healing	-
	hmark control, a non-marketed adhesive bandage
benchmark control, four non-marketed adhesive bar	dages, and no treatment (uncovered, negative
control).	
	d, bandage changes will be discontinued and the
wound will be left uncovered.	
All and the all the second for a Be 46 to Be 2	
All wound sites will be uncovered from Day 16 to Day 2	8, at which point subjects will return for a scar
assessment of each wound site ⁵ , and	
Con costion 7 for datailed are and uses	
See section 7 for detailed procedures.	

4. SUBJECT SELECTION AND ENROLLMENT

This study can fulfill its objective only if appropriate subjects are enrolled. The eligibility criteria are designed to select subjects for whom protocol procedures are considered appropriate.

All relevant medical and non-medical conditions should be taken into consideration, in addition to the inclusion/exclusion criteria below, when deciding if a particular individual is suitable for this protocol.

Different Adhesive Bandages Protocol Number: CCSTOH001689

Version & Date: Amendment 3: Final Version 4.0, 28 Aug 2019

No type of discrimination (e.g. social class, gender, skin color, ethnicity, etc.) should preclude an eligible subject from participating in the study. Information that is not relevant to the conduct of the study should not be collected.

Prior to any review of personal data, the Informed Consent Document (ICD) should be signed.

4.1. INFORMED CONSENT

The ICD must be read by the subject and explained to the subject by the PI or designee.

The PI or designee must ensure that each study subject is fully informed about the nature and objectives of the study and possible risks associated with participation. After understanding and agreeing, the subject will express his/her consent to his/her participation in the study by signing the ICD.

The ICD will be signed and dated by both the PI/designee and by the subject. The signed and dated original will be kept in the Site Master File (SMF) and a signed and dated copy must be given to the subject.

No subject will be evaluated without a signed and dated ICD, which should be kept by the PI/Site as part of the SMF. The ICDs of subjects who are not included in the study will also be part of the SMF.

The ICD must be approved by the Sponsor and the Institutional Review Board/Independent Ethics Committee (IRB/IEC) and must be in compliance with the principles of ICH GCP, local regulatory requirements, and legal requirements.

4.2. STUDY POPULATION

The PI must ensure that an individual meets all the inclusion criteria and none of the exclusion criteria to be included in the study. Waivers to inclusion or exclusion criteria are not permitted. In addition, the PI or designee must ensure that the subject remains eligible through the entire study conduct.

The initial verification of eligibility, including review of medical history and concomitant medications, may be conducted by a non-medically qualified individual (PI or designee).

The eligibility must then be reviewed and confirmed by a medically qualified individual (the Study Physician) before enrollment. The medically qualified individual is not required to review the eligibility information if the potential subject is screen-failed by the non-medically qualified staff.

4.2.1. Inclusion Criteria

- a) Male or female
- b) 25 to 55 years old
- c) Fitzpatrick Skin Type II or III (see Appendix I)
- d) Uniform skin color on both volar forearms.
- e) Generally in good health based on medical history reported by the subject.
- f) Able to read, write, speak, and understand English.

Protocol Number: CCSTOH001689

Version & Date: Amendment 3: Final Version 4.0, 28 Aug 2019

- g) Individual has signed the Consent for Photograph Release and ICD including Health Insurance Portability and Accountability Act (HIPAA) disclosure.
- h) Has access to a computer or phone with internet access and the ability to complete online questionnaires.
- Willing to have temporary (semi-permanent) dot-tattoos applied to the volar forearms.
- j) Willing to undergo topical anesthetic and laser wound treatment on the volar forearms.
- k) Intends to complete the study and is willing and able to follow all study instructions (see section 4.2.3).

4.2.2. Exclusion Criteria

- a) Has known allergies, hypersensitivity, or adverse reactions to anesthetics, adhesive bandages, latex, wound treatment products, or any component/ingredient present in the IPs/auxiliary/ancillary products.
- b) Has a known history of a blood-clotting disorder, keloid formation, or a cardiovascular, hepatic, or renal disease.
- c) Presents with a skin condition that would, in the opinion of the PI or Study Physician, confound the study results, increase risk to the subject, or interfere with study evaluations (e.g., active psoriasis, seborrheic dermatitis, atopic dermatitis, skin dermatoses, keloids, hypertrophic scars, cracked/excoriated skin, acne scars, pigmentation, friable skin, or clinically infected skin lesions).
- d) Has excessive hair or tattoos on either volar forearm.
- e) Has a known history of severe systemic immune system disorders such as Systemic Lupus Erythematosus (SLE), Rheumatoid Arthritis (RA), Scleroderma, chronic connective tissue disorders, Poly Arteritis Nodosa, or immunodeficiency, including HIV infection.
- f) Has self-reported Type 1 or Type 2 diabetes or is taking insulin or another anti-diabetic medication.
- g) Has self-reported uncontrolled chronic diseases such as hypertension, hyperthyroidism, hypothyroidism, or active or recently treated (within 1 year) skin cancer.
- Is taking a medication that would mask an Adverse Event (AE), confound the study results, or alter or compromise the bleeding/healing process including:
- Antibiotics, corticosteroids, immunosuppressive agents, anti-coagulants, antiplatelet drugs, cytotoxic
 agents, continuous aspirin therapy, chemotherapy, or daily medications for chronic asthma, within 1
 month before Visit 1.*
- Non-steroidal anti-inflammatory drugs or steroidal drugs within 5 days before Visit 1.* Low dose aspirin (81 mg per day) is allowed.
- Antihistamines within 2 weeks before Visit 1.*
 - * If an individual is taking one of these medication types, the individual is not considered eligible at screening. However, if a subject begins using one of these medications during the study, the Study Physician should be consulted to consider the impact of the specific medication on subject safety and/or the study results as described in section 0 ("Concurrent/Concomitant Medication").
- i) Is self-reported to be pregnant or planning to become pregnant during the study.

Protocol Number: CCSTOH001689

Version & Date: Amendment 3: Final Version 4.0, 28 Aug 2019

- j) Has taken/used (oral or topical) vitamin A derivatives such as Accutane, isotretinoin, or retinoic acid within the past 1 year.
- k) Has used topical leave-on products on the volar forearms within 1 week prior to Visit 1.
- Is participating or has participated in 1) any clinical trial involving a topical or systemic investigational drug within 30 days prior to Visit 1 or 2) any other clinical study within 10 days prior to Visit 1.
- m) Has a body mass index (BMI) above 35 on the BMI scale (see Appendix II), based on the subject's self-reported height and weight.
- n) Is self-reported to be an alcohol or drug abuser.
- o) Is an employee/contractor or immediate family member of the PI, Study Site, or Sponsor.
- Either is or lives with someone who is a current employee of any company that makes or markets adhesive bandages or first aid products.
- q) Has a history of or a concurrent health/other condition/situation which may put the individual at significant risk, confound the study results, or interfere significantly with the individual's participation in the study.

4.2.3. Subject Responsibilities

During the study, the subject should follow the instructions below:

- Use the provided cleanser on your forearms and body for the duration of the study in place of your normal body cleanser. Do not use any other products on your forearms during the study.
 For the rest of the body, continue using your normal skincare products; do not start using any new products/brands.
- Do not wet or put your forearms in water for the duration of the study (i.e., swimming, baths, hot tubs, etc.). Only showering is acceptable.
- Do not shower within 2 hours before a visit.
- Do not expose the test sites to sunlight or use tanning booths/beds during the study.
- Wear long sleeves when going outdoors and for the first 12 hours after each tattoo application (ink may transfer to other skin locations).
- Avoid touching/scratching the test sites.
- Leave the test products (the bandages) on your forearms only the study site should remove or apply them. If the bandages become loose between clinic visits, you may use the provided tape to secure the bandage; apply the tape only on the adhesive parts of the bandage (not on the pad or middle of the bandage).
- If any test product (bandage) falls off, record the date and time that the bandage fell off and report that information at your next visit. Do not try to reapply any bandage if it falls off. Please bring the bandage that has fallen off to your next visit.
- Whenever possible, inform the study team before you start using any new medication.
- Avoid pregnancy by continuing to use a medically acceptable contraception method, if applicable.
- Attend all study visits at the scheduled time and date.
- Do not start any other studies during this study.

Different Adhesive Bandages Protocol Number: CCSTOH001689

Version & Date: Amendment 3: Final Version 4.0, 28 Aug 2019

4.3. CONCURRENT PRODUCTS

Subjects should use only the provided auxiliary cleanser on their forearms and body in place of their normal body cleanser. They should not use any other products on their forearms during the study (other than the auxiliary product and IPs). For the rest of their body, they should continue using their normal skincare products and not start using any new products/brands.

4.4. CONCURRENT/CONCOMITANT MEDICATION

If a subject is taking any medication during the course of the study and/or within 4 weeks prior to the study, it must be recorded. The minimum information that is required is the name of the medication.

If this medication is linked to the treatment of an IP-related or study-related AE, the dose and duration of the treatment should be specified.

Medications excluded are indicated in the section "Exclusion Criteria"; if a subject begins using an excluded medication during the study, the Study Physician must consider whether it will impact the subject's safety and/or confound study results and document the decision. In case of impact, the subject should be discontinued.

4.5. SCREEN FAILURE

All individuals who sign the ICD and withdraw their consent for participation in the study or fail to meet at least one of the eligibility criteria during the initial evaluation will be considered a "screen failure" and their data will be entered in the Electronic Data Capture (EDC) system and the AEs will be included in the final report.

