6.6. RANDOMIZATION/IP ALLOCATION AND BLINDING

Upon signing the ICD, each subject will be sequentially issued an eight-digit subject ID. The first four digits will be the center ID, 1001, and the next four digits will be a unique subject identifier assigned in ascending numerical order beginning with 1001 (i.e. subject ID 10011001, 10011002, 10011003, etc.).

Different Adhesive Bandages Protocol Number: CCSTOH001689

Version & Date: Amendment 3: Final Version 4.0, 28 Aug 2019

Qualified subjects will be assigned a randomization number sequentially from the randomization list at the Baseline visit (Visit 2). Once a randomization number has been assigned to a subject, it cannot be reassigned to another subject.

Randomization of the study treatments to the eight wound sites (see section 7.2.3.3; one study treatment per wound site) will be based on a randomization scheme devised by the Biostatistics Group at the Sponsor using assigned treatment codes (A through H).

Due to the nature of the IPs and the study design, it is not feasible to fully blind the IPs or to conceal the treatment assignments from study subjects or from all study personnel (i.e. those involved in applying/removing the IPs, IP accountability, or assessing subject compliance). Staff responsible for IP accountability and IP application/removal (hereafter "unblinded staff") will have access to the randomization schedule in order to accurately administer the study treatments. The unblinded staff will not complete any subject evaluations other than the interview for compliance/AEs.

The PI and staff conducting evaluations other than the interview for compliance/AEs (hereafter "blinded staff") will not have access to the randomization schedule, and the IPs will be kept separate from the blinded staff. Subjects will be instructed not to disclose information about their assigned study treatments to blinded staff, or to discuss any other information that may reveal the treatment assignment.

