7. INVESTIGATIONAL PLAN

7.1. STUDY DURATION

The study will consist of 20 visits over approximately 5 weeks with visits scheduled at Screening (Visit 1, 3 to 7 days prior to Visit 2), Day 0 (Visit 2, Baseline/Pre-Wound and Post-Wound time points), daily on Days 1 through Day 16 (Visit 3 through Visit 18), Day 21 (Visit 19), and Day 28 (Visit 20). A subject's Day 0 through Day 28 study visits should be scheduled at approximately the same time of day for each visit (i.e., morning, afternoon, or evening).

Version & Date: Amendment 3: Final Version 4.0, 28 Aug 2019

STUDY PROCEDURES AND EVALUATION SCHEDULE 7.2.

The table below presents a summary of the study procedures and evaluation schedule.

Table 2. Schedule of Events

	:	1	2 -	2	(-	,	7, 9, 11,	8, 10,	,	ļ	,	,	(
Procedures:	Visit:	Screening	Baseline (Pre-Wound)	(Post- Wound)	3 & 4	5	9	13, & 15	12, & 14	16	17	18	19	20
	Day:	-7 to -3	0	0	1 & 2	3	4	5, 7, 9, 11 & 13	6, 8, 10 & 12	14	15	16	21	28
ICD with HIPAA disclosure & Photo Release	4)	×												
Demographics, medical history, and conmeds collection	spe	×												
Review of eligibility/enrollment		×												
Dispense auxiliary cleanser & study instructions	tions	×												
Interview for compliance and changes in			*	X	X	X	X	×	×	×	X	X	×	×
health/AEs/conmeds			·	(AEs only)	<	`	`	,	·	`	<	<	~	<
Randomization			×											
			×	×	×	×	×	×	×	×	×	×	×	
Test site label application			×	×	×	×	×	×	×	×	×	×	X	×
IP Removal					AX	×	X^B	×	XB	χ_{B}	X	X		
5-min acclimation			×	×	ЯX	×	X^B	×	X _B	XB	X	X		×
Clinical grading of wound healing parameters	ers		×	×	X_B	×	X^B	×	XB	XB	×	×		
Scarring assessment			×											×
			×	×	A^B	×	X^B	×	XB	χ_{B}	X	X	X	×
			×	×	A^B	×	X^B	×	XB	XB				
TEWL measurements			×	×	яΧ	×	XB	×	X _B	XB				
			×					X_D	(×
BLT cream application (30 min prior to wounding)	ding)		×											
Test site cleaning and wounding			×											
IP application ^E				×	X _B	×	X^B	X	XB	χ_{B}	X			
Subject self-assessment questionnaire				Xc	×	×	×							
Collect auxiliary product														×
										1	1	1	1	Ī

^cAssessment will be completed remotely approximately 3-4 hours after BLT cream application once numbness is gone.

 $^{^{\}text{D}}\text{At}$ time of complete healing for a particular wound site. $^{\text{E}}\text{Completely}$ healed wound sites will be left uncovered for the remainder of the study.

Version & Date: Amendment 3: Final Version 4.0, 28 Aug 2019

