7.2.2.3. Distribution of Auxiliary Cleanser

Enrolled subjects will be provided with a unit of the auxiliary cleanser along with written and verbal study instructions (Appendix III).

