10.3.3. Procedures for Reporting AEs

All AEs will be reported from the time a signed and dated ICD is obtained until completion of the subject's last study procedure or visit (or termination if the subject terminates early from the study for any reason).

AEs that occur within 30 calendar days after completion of the study will only be reported to the Sponsor if they are serious (i.e. SAEs). SAEs are reportable beyond this period if the event is considered study-related. The Sponsor will evaluate any safety information that is spontaneously reported by the PI/Site beyond this time frame.

Subjects are encouraged to report AEs spontaneously and in response to questioning during the visit (e.g. if they have had any side effects/issues or changes in their health since their last appointment). For each AE reported by the subject or observed by the Site team, the Site team member should notify the PI or designee, who will collect information about the event.

All AEs, regardless of seriousness, severity, or presumed relationship to study procedures, must be recorded using medical terminology. Whenever possible, diagnoses should be given when signs and symptoms are due to a common etiology (e.g., cough, runny nose, sneezing, sore throat, and head

Different Adhesive Bandages Protocol Number: CCSTOH001689

Version & Date: Amendment 3: Final Version 4.0, 28 Aug 2019

congestion should be reported as "upper respiratory infection"). The Study Physician must record or confirm their opinion concerning the seriousness, severity, and relationship of the AE to the study. All measures required for AE management must be recorded and reported according to Sponsor instructions.

These events must then be entered into the EDC system within 3 business days of the Site's awareness.

Tabulation of AEs

AEs will be reported in a table detailing the different AE types highlighted in this protocol:

- Pre-Treatment AEs (PTAEs)
- Expected AEs
- AEs related to the product(s)/study
- AEs not related to the product(s)/study
- SAEs related to the product(s)/study
- SAEs not related to the product(s)/study

Additional Reporting Procedures

The PI or designee must also report AEs to the appropriate IRB/IEC unless otherwise required and documented by the IRB/IEC.

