6.5 SAFETY ANALYSIS

All subjects who have IP applied at least once will be included in the safety analysis. All AEs reported during the AE reporting period will be listed by subject number.

The number and percentage of subjects experiencing treatment-emergent adverse events will be presented by body system and preferred term. Treatment-emergent adverse events are those with a start date and time on or after the date and time of first use of investigational product, or the AEs started before the first use of investigational product and worsened after it. The latest version of the Medical Dictionary for Regulatory Activities (MedDRA) will be used as the adverse event classification system.

Number and percentage of subjects with serious adverse events will be summarized by MedDRA system organ class and preferred term.

Number and percentage of subjects with treatment-related adverse events will be summarized by MedDRA system organ class and preferred term. Treatment-related AEs are events evaluated by the investigator as possible, probable or very likely related to

Protocol CCSTOH001689
Statistical Analysis Plan

investigational product. AEs with unknown relationship to treatment will be considered as treatment-related.

APPENDICES

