APPENDIX 2: DATA LISTINGS

The following listings are planned for subsections in Appendix of Clinical Study Report. The numbering and titles of data listings in this document serve as guidance; the exact numbers and titles may be modified as appropriate.

Listing No.	Title	Population
16.1.7	Randomization Scheme and Codes	All randomized Subjects
16.2.1.1	Subject Disposition Listing	All randomized Subjects
16.2.1.2	Discontinued Subjects	All randomized Subjects
16.2.2	Subjects with Protocol Deviations	All randomized Subjects
16.2.3	Subjects Excluded from the Primary Analysis	All randomized Subjects
16.2.4.1	Demographic and Baseline Characteristics	All randomized Subjects
16.2.6.1	Clinical Grading of Wound Healing Parameters Measurements	All randomized Subjects
16.2.6.2	Trans Epidermal Water Loss (TEWL) Measurements	All randomized Subjects
16.2.6.3	Manchester Scarring Assessment Measurements	All randomized Subjects
16.2.6.4	Self-Assessment Questions	All randomized Subjects
16.2.7.1	Subjects with Adverse Events	All randomized Subjects
16.2.7.2	Subjects with Serious Adverse Events	All randomized Subjects
16.2.7.3	Subjects Withdrawn from Investigational Product due to Adverse Events	All randomized Subjects

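### No table or listing specified in the SAP appendices can show adverse events of people who consented but were not randomized, although the Protocol promises to report them

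*Protocol*

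**What the plan says.** **Protocol.** Section 4.5 defines a screen failure as someone who signs the consent document and then withdraws consent or fails an eligibility criterion at the initial evaluation. For these people "their data will be entered in the Electronic Data Capture (EDC) system and the AEs will be included in the final report". Section 10.3.3 sets the start of collection: "All AEs will be reported from the time a signed and dated ICD is obtained". Section 8.4 says that all AEs of that period are listed by subject number. Section 6.6 assigns the randomization number at Visit 2, and section 7.1 places Screening 3 to 7 days before that visit. Study material is in use in between, because section 7.2.2.3 states that "Enrolled subjects will be provided with a unit of the auxiliary cleanser" at Visit 1.

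**SAP.** Section 6.5 repeats the listing commitment: "All AEs reported during the AE reporting period will be listed by subject number". Section 3.3 defines the Safety Analysis Set as subjects with at least one IP application, and Appendix 1 assigns Tables 14.3.1, 14.3.2 and 14.3.3 to that set. In Appendix 2, Listing 16.2.7.1 ("Subjects with Adverse Events"), Listing 16.2.7.2 (serious events) and Listing 16.2.7.3 (withdrawals from IP because of AEs) all have randomized subjects as their population.

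**The concern.** The commitments run from consent, while the outputs that should deliver them begin at randomization or later. An event between those two points, in someone who never reaches randomization, is collected and entered in the EDC system. No output named in the SAP then retrieves it. A programmer who follows Appendix 2 will filter on randomization status, and a report author who relies on those listings could show no pre-randomization events or SAEs when the database holds some.

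The interval is not free of exposure. Protocol section 6 counts the auxiliary cleanser among the investigational study materials, and enrolled subjects receive it at Visit 1. A subject who reacts to it and leaves before Day 0 would be missing from every AE and SAE output in the appendices. What is at stake is completeness of safety reporting. The healing-time analysis and the secondary efficacy comparisons do not depend on it.

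**Working it through.** There is no planned figure to reproduce. The check compares each output's population with the order of study events.

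**Order of events.** Consent at Visit 1 starts AE reporting (Protocol 10.3.3). The cleanser is dispensed to enrolled subjects at Visit 1 (7.2.2.3). Randomization follows at Visit 2, Day 0, 3 to 7 days later (6.6, 7.1). IP is first applied on Day 0 after wounding (7.2.5.2).

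**Outputs against that order.**

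| SAP output | Population | Requires | Can include consented, not randomized? |
|---|---|---|---|
| Table 14.3.1 | Safety Analysis Set | IP application | No |
| Table 14.3.2 | Safety Analysis Set | IP application | No |
| Table 14.3.3 | Safety Analysis Set | IP application | No |
| Listing 16.2.7.1 | Randomized | Randomization | No |
| Listing 16.2.7.2 | Randomized | Randomization | No |
| Listing 16.2.7.3 | Randomized | Randomization | No |

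Count: 3 tables + 3 listings = 6 outputs, of which 0 can include such a person.

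**Who falls in the gap, and which commitment covers them.**

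1. *Fails eligibility at Visit 1.* Covered by Protocol 4.5. This person is not enrolled and does not receive the cleanser.
2. *Enrolled, then withdraws consent before Day 0.* Covered by Protocol 4.5 if its words on withdrawal of consent extend past Visit 1, and by Protocol 8.4 and SAP 6.5 read with 10.3.3. This person has the cleanser.
3. *Enrolled, then stopped before Day 0 for another reason, such as an AE.* Not clearly a screen failure: section 7.6.2 lists AEs and ineligibility found after enrollment separately from screen failure. The commitment here rests on Protocol 8.4 and SAP 6.5 read with 10.3.3.
4. *Randomized but never given IP.* Outside the gap, since Listings 16.2.7.1 and 16.2.7.2 include this person.

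**Number affected.** The documents do not say how many people will be screened. Enrollment of up to 40 with 30 completers allows for 40 − 30 = 10 losses at any stage. That is neither an estimate of losses before Day 0 nor a bound on them, because section 7.6.2 allows additional enrollment. Visit 1 screen failures would be extra. No count can be derived.

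**The case against.** The strongest reply is that the documents already state the right rule. Protocol 8.4 and SAP 6.5 promise a listing of all AEs in the reporting period, Protocol 10.3.3 calls for a table by AE type that includes pre-treatment AEs, and Protocol section 15 requires the final report to describe any AEs. SAEs also go to the sponsor at once and AEs to the IRB/IEC. It would therefore be too strong to infer that these events will go unreported, or that no planned output of any kind covers them. That part of the reply stands, and the claim here is limited to the tables and listings specified in the SAP appendices.

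The reply does not remove the conflict. The listings that would carry out the general sentence exclude the people in question, and the SAP has no table matching the one in 10.3.3. In both Protocol 8.4 and SAP 6.5 the general sentence directly follows one limiting the safety analysis to subjects with IP applied. If it is read within that limit, it gives these people no cover at all, and Protocol 4.5 remains unserved for screen failures. The appendix note lets numbers and titles be modified and does not mention populations.

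Two further inferences go beyond the documents. One is that the cleanser goes to everyone who consents; it goes to enrolled subjects only. The other is that Protocol 4.5 requires reporting for everyone who leaves before Day 0; that is not established for an enrolled subject stopped for an AE. Nor do the documents give any rate of cleanser reactions or early dropout, and known hypersensitivity to its ingredients is an exclusion (4.2.2).

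**Conclusion.** The point holds as an inconsistency between the SAP appendices and the reporting commitments in Protocol 4.5, Protocol 8.4 and SAP 6.5. It follows from the stated populations and the timing of randomization, with no outside assumption. For enrolled subjects who are not screen failures, it also assumes that the general listing sentence means every AE from consent onward.

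Severity is minor. The people affected may be few or none, AE collection and expedited reporting are intact, and no efficacy estimate or test changes. It is still worth correcting, because the listings as labelled leave out events that the Protocol says will be reported.

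**What to change.** In SAP Appendix 2, change the population of Listings 16.2.7.1 and 16.2.7.2 to all subjects who signed the informed consent document, and add a column flagging those not randomized. Keep Tables 14.3.1 to 14.3.3 on the Safety Analysis Set.

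Extending disposition Listings 16.2.1.1 and 16.2.1.2 in the same way is optional, because Protocol 7.6.2 already puts the reasons for non-inclusion and discontinuation in the final study report. While the SAP is open, the authors could also say where the by-type AE table of Protocol 10.3.3, with its pre-treatment row, will be produced.

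The cost is one population label and one filter for two listings. No new data are needed: Protocol 4.5 puts screen-failure data in the EDC system, and section 12 calls for EDC pages for each enrolled subject. The only downside is a slightly longer listing.
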